3.2. Study Endpoints

3.2.1. Efficacy Endpoint

3.2.1.1 Primary Efficacy Endpoint

The nasal symptom score (NSS) for a subject and time point will be calculated as the sum score of the nasal symptoms (blocked nose, runny nose, and sneezing) at that time point. The primary efficacy endpoint is average nasal symptom score across Days 1 to 4 (ANSS₁₋₄).

3.2.1.2 Secondary Efficacy Endpoint

The secondary efficacy endpoints are as follows:

- average nasal symptom score Days 1-7 (ANSS₁₋₇), derived as the mean of the daily NSS across study Days 1 to 7.
- average total symptom score Days 1-4 (ATSS₁₋₄), derived as the mean of the daily TSS across study Days 1 to 4.
- average total symptom score Days 1-7 (ATSS₁₋₇), derived as the mean of the daily TSS across study Days 1 to 7.

3.2.2. Exploratory Efficacy Endpoints

- Individual & composite total symptom scores (NSS and TSS) Days 1-7

3.2.3. Safety Endpoints

- Spontaneous and solicited adverse events and serious adverse events

3.3. Treatments

The study treatment is called 1146A formulation (CCI carbomer 980 gel) nasal spray. The control is called placebo (vehicle without carbomer 980) nasal spray. Subjects will apply the dose by alternating nostrils. Both treatments will be administered via a nasal spray device (1 dose =3 actuations per nostril, each actuation is 140 μ L). Dosing administration is 3 actuations per nostril per dose, four times a day for 7 days (except for Day 1 where subjects in the 2nd strata will receive 3 doses).

3.4. Dose Adjustment/Modifications

No dose modification is permitted in this study.

4. General Statistical Considerations

Continuous data will be summarized by descriptive statistics showing the number of subjects (N), the mean, standard deviation (SD), median and minimum and maximum. Categorical data will be summarized by frequency tables showing the number and percentage of subjects falling into each category. When count data are presented, the percentage will be suppressed when the count is zero in order to draw attention to the non-zero counts. The denominator for all percentages will be the number of subjects in that treatment within the analysis set of interest, unless otherwise specified.

For the summary statistics of all numerical variables unless otherwise specified, minimum and maximum will be displayed to the same level of precision as reported. Mean and median will be displayed to one level of precision greater than the data collected. Standard deviation will be displayed to two levels of precision greater than the data collected. P-values will be rounded to three decimal places. If a p-value is less than 0.001 it will be reported as “<0.001.” If a p-value is greater than 0.999 it will be reported as “>0.999.” Data will be displayed in all listings sorted by treatment group.

Unless otherwise specified, baseline will be defined as the last non-missing evaluation prior to or on the date that the first dose of treatment is taken. The study day will be calculated as assessment date - first dose date of double-blind study drug + 1.

All analyses will be conducted using SAS Version 9.3 or higher.

A two-sided test for primary analysis of the primary efficacy endpoint will be used at a Type I error rate of 0.05 for comparison between active group (i.e., 1146A formulation) and control group. The p-values reported for sensitivity analyses of the primary efficacy

endpoint and statistical analyses of the secondary efficacy endpoints and the exploratory efficacy endpoints will not be adjusted for multiplicity and will be considered nominal.

4.1. Definition of Baseline and Study Day

Baseline is defined as the latest assessment prior to the first dose of treatment on Day 1, i.e., Day 1 Assessment 1. If a baseline measurement is missing or the subject receives the first dose prior to Day 1 Assessment 1, and a Screening value is available, the Screening value is utilized as the baseline. For assessments on or after Day 1, the study day will be calculated as assessment date – date of treatment (Day 1) + 1. For assessment prior to Day 1, the study day will be calculated as assessment date – date of treatment (Day 1).

4.2. Sample Size

Upon review of the most recent literature (Fazekas et al 2012, Ludwig et al 2013, and Eccles et al 2015), similar studies employing the use of nasal spray products with a similar purported mechanism of action had sample sizes between 153 and 211. Therefore, an approximate sample size of 170 (85 subjects in each treatment group) is considered sufficient for this study.

A sufficient number of subjects will be screened to enroll approximately 170 subjects.

4.3. Randomization, Stratification, and Blinding

Subjects will be assigned to one of two treatment groups (1146A or placebo) using the method of randomly permuted blocks with a fixed block size in accordance with the stratified randomization schedule. The sites will not receive the randomization schedule, but will be assigned blocks of randomization numbers generated from the IRT system. All site personnel will be blinded to the treatment allocations. GSK and PPD personnel who may influence study outcomes are kept blinded to the treatment allocations.

Subjects who meet all inclusion and exclusion criteria will be randomized to one of the two treatment groups (1146A or placebo) in a 1:1 allocation ratio. The IRT system will randomize and stratify by site and by dosing time on Day 1. The maximum number of subjects each site can randomize will be capped at 26 (15% of the target number of randomised subjects). This is to ensure that the study population is reasonably distributed across as many sites as possible, and not dominated by one or two sites providing the majority of subjects.

4.4. Analysis Population

The following analysis populations are defined:

4.4.1. Intent-to-Treat (ITT) Population

Intent-to-Treat (ITT) population will consist of all randomized subjects.

In the event there is a discrepancy between treatment received and randomized treatment, all subjects in the ITT set will be analyzed according to the treatment they were randomized to receive and not according to what they actually received.

4.4.2. Modified Intent-to-Treat (mITT) Population

The mITT population includes subjects who received at least one dose of study medication and have at least one post-baseline efficacy assessment. The mITT will be used for all primary, secondary and exploratory efficacy analyses.

In the event there is a discrepancy between treatment received and randomized treatment, all subjects in the mITT population will be analyzed according to the treatment they were randomized to receive and not according to what they actually received.

4.4.3. Safety (SAF) Population

The SAF population will include all randomized subjects who received at least one dose of study medication.

All subjects in the SAF population will be analyzed according to the treatment actually received and not according to the treatment they were randomized to receive, in the event there is a discrepancy. The SAF population is used to tabulate all of the safety endpoints.

4.4.4. Per Protocol (PP) Population

The Per-Protocol (PP) population will be determined from compliance during Days 1 to 4, since this is the period of the primary efficacy evaluation.

Any randomized subjects who violated the following inclusion or exclusion criteria will be reviewed on a case by case basis to determine whether they should be excluded from the PP population.

In addition, any subjects who violated the following criteria will be excluded from the PP population.

- a. Subjects who complete less than 80% or more than 120% of their target number of actuations over Days 1 to 4
- b. Subjects who miss 2 or more doses on any one day during Days 1 to 4
- c. Subjects who miss a total of 4 or more of their doses during Days 1 to 4

- d. Subjects who miss more than 1 nasal assessment on any one day during Days 1 to 4.
- e. Dosing outside of allowable time window (2 or more times on any day during Days 1-4)
- f. Use of prohibited medications during Days 1 to 4 as listed in the protocol
- g. Dosing more than 5 minutes prior to self-assessments of symptoms using the eDiary device at home. This is because dosing time is entered manually and can only allow entrance in the increments of 5 minutes. The manual time to be entered has to be in the past. Since the time for dosing has to be in the past and only in 5 minute increments, subjects may have entered a time for dosing that is earlier than automatic time for symptoms assessments.

Analysis on the PP population will be used as a supplement to the mITT analysis and will be performed for the primary efficacy endpoint average nasal symptom score Days 1-4 (ANSS₁₋₄) and the secondary efficacy endpoint average total symptom score Days 1-4 (ATSS₁₋₄).

5. Subject Disposition

5.1. Disposition

Subject disposition will be summarized for the population of all screened subjects by treatment group and overall. A disposition of subjects includes the number and percentage of subjects for the following categories: subjects randomized, subjects who completed the study, subjects who discontinued from the study, subjects in the ITT population, subjects in mITT population, subjects in the SAF population, and subjects in the PP population. All percentages will be based on the number of subjects randomized.

The number and percentage of subjects' study completion/termination status and the categories of study completion/termination status will be displayed in the order they are displayed in the CRF as follows:

- Subject did not meet study criteria
- Protocol violation
- Withdrawal of informed consent
- Unblinding of the subject
- Subject lost to follow-up
- Pregnancy
- Death

- Adverse event
- Other

Subject disposition data will also be presented in a listing. A listing of screen fail subjects will be also provided. Screen failures are defined as subjects who did not meet one or more criteria required for participation in a trial.

5.2. Protocol Deviations

Protocol deviation is defined as non-compliance with the protocol/ICH-GCP which may impact subject rights, safety or well-being, or the integrity of the data:

- Significant Deviation: Non-compliance with the protocol/ICH-GCP which significantly impacts subject rights, safety or well-being, or the integrity of the data.
- Non-Significant Deviation - Non-compliance with the protocol/ICH-GCP which does not significantly impact subject rights, safety or well-being, or the integrity of the data.

The significant protocol deviations are defined in Appendix C by the study team and will be finalized before database lock.

All protocol deviations including protocol deviations leading to exclusion from the Per Protocol population will be presented in a listing. The subject data listing will be sorted by site, subject number, and treatment group. Potentially important protocol deviations will be summarized in the clinical study report.

6. Demographics and Baseline Characteristics

6.1. Demographics

The following demographic parameters will be captured by the Investigator or designee and recorded in the CRF: age (years), gender, race and ethnicity.

Age (years) will be summarized using descriptive statistics. The number and percentage of subjects by age category (<65 vs. ≥ 65), gender (Male, Female), race (White, Black or African American, Asian, American Indian or Alaska Native, Native Hawaiian or Other Pacific Islander, other), and ethnicity (Hispanic or Latino, Not Hispanic or Latino) will also be reported.

Demographic characteristics will be summarized descriptively by treatment group and overall for the Safety population. The demographic characteristics will also be summarized

by center as a subgroup. Percentages will be based on the total number of subjects in the Safety population. Subject demographic data will also be presented in a listing.

6.2. Baseline Disease Characteristics

Baseline characteristics will be summarized descriptively by treatment group and overall for the Safety population. Baseline characteristics will also be summarized by center as a subgroup. Baseline characteristics include the following:

- Total Symptom Score (TSS)
- Severity grading of the symptoms common cold as follows:

Nasal symptoms:

- runny nose
- blocked nose
- sneezing

Other symptoms

- headache
- muscle ache
- chills
- sore throat
- cough

Subject baseline disease characteristics will be presented in a listing.

6.3. Medical History

Medical history will be listed.

6.4. Inclusion and Exclusion Criteria

The subjects who fail to meet the inclusion/exclusion criteria will be listed. Please refer to Protocol Sections 4.1 and 4.2 for details of with inclusion/exclusion.

7. Treatments and Medications

7.1. Prior and Concomitant Medications

Details of any relevant medical or surgical history, including allergies or drug sensitivity, will be recorded in the CRF. Wherever possible, diagnoses and not symptoms will be recorded. Any medication and non-drug therapies/procedures therapy taken in the 90 days

prior to the Screening Visit will also be recorded. Relevant history will be recorded in the CRF.

For purposes of analysis, prior medications are defined as any medication with a stop date that is prior to the initial study drug dosing date and concomitant medications are defined as any medications with a start date on or after the initial study drug dosing date, but prior to the last study drug dosing or any medications with a start date prior to the initial study drug dosing date and a stop date after the initial study dosing date.

For medications with partial start or stop dates, the partial dates will be imputed according to Table 1 and then will be categorized as prior medication or concomitant medication according to the definitions. Medications with completely missing dates will be included in the concomitant medication summary.

Imputation rules for the start or stop date of missing or incomplete medications are presented in Table 1.

Any changes in concomitant medication or non-drug treatments/procedures will be recorded in subject's e-diary and will also be captured in the CRF. There will be a specific question in the e-diary asking about acetaminophen/paracetamol and all other concomitant medication usage prior to each dose of study treatment.

The number and percentage of subjects receiving prior and concomitant medications will be displayed by medication classes (levels 1 and 2) of the Anatomical Therapeutic Chemical (ATC) classification system and by treatment group using Safety set. A listing of all medications taken by subjects, including those are only prior, will be produced.

Table 1. Imputation rules for the start or stop date of missing or incomplete medications

	Missing	Imputation	Exception
Start date (concomitant medication)	Day	01	Default to Study Day 1 if an event starts the same year and month as Day 1 and the stop date contains a full date and the stop date is later than Day 1; Otherwise If the stop date is prior to Day 1, default to 1 day prior to the stop date
	Day/Month	01Jan	Default to Study Day 1 if an event started the same year as Day1 and the stop date contains a full date and the stop date is later than Day 1; Otherwise If the stop date is prior to Day 1, default to 1 day prior to the stop date
	Day/Month/Year	No imputation	Assume start prior to study entry.
Stop date (concomitant medication)	Day	Last day of the month	Default to the End of Study Date if the concomitant medication stopped the same year and month as the End of Study Date.
	Day/Month	31DEC	Default to the End of Study Date if the concomitant medication stopped the same year as the End of Study Date.
	Day/Month/Year	No imputation	Assume stops after study end.

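### Under SAP 7.1 a medication started before the first dosing date and stopped on that date is neither prior nor concomitant, so both by-arm summary tables omit it

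*SAP*

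**What the plan says.** SAP 7.1 sorts medications by comparing their start and stop dates with the dosing dates.

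- Prior: "prior medications are defined as any medication with a stop date that is prior to the initial study drug dosing date".
- Concomitant, first branch: "any medications with a start date on or after the initial study drug dosing date, but prior to the last study drug dosing".
- Concomitant, second branch: "any medications with a start date prior to the initial study drug dosing date and a stop date after the initial study dosing date".

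Two further rules deal with incomplete dates. "Medications with completely missing dates will be included in the concomitant medication summary". Where a date is only partly known, "the partial dates will be imputed according to Table 1 and then will be categorized as prior medication or concomitant medication according to the definitions".

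On reporting, the section states: "The number and percentage of subjects receiving prior and concomitant medications will be displayed by medication classes". This is done by treatment group on the Safety set. The same section also plans a listing of every medication taken. Protocol 9.3.5.2 plans the concomitant summary by class and arm, but gives no date rule of its own.

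**The concern.** For a medication that began before the first dosing date, the two definitions should divide all possible stop dates between them. They leave out one date: the first dosing date itself. In this trial that date is also the day of screening and randomization (Schedule of Events), so it is a date that can appear on a medication record.

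A programmer who applies the rule literally drops these records from both tables. One who notices the gap has to choose a rule that the SAP does not document. Either way the by-arm class counts would not match a plain reading of what was taken up to and during treatment.

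**Working it through.** **Inputs** (all from SAP 7.1). Let F be the first dosing date and L the last. For one record, s is the start date and e the stop date.

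- Prior: e < F
- Concomitant, branch 1: F ≤ s < L
- Concomitant, branch 2: s < F and e > F

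The plan states no figure to reproduce. The check is whether these conditions cover every record.

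**Enumeration.** Set F = 1 and L = 7 on a plain calendar-day count, with 0 as the day before first dose. All pairs with s from −5 to 10 and e from s to 12 were classified. For starts before F (s from −5 to 0) there are 18 + 17 + 16 + 15 + 14 + 13 = 93 pairs:

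| Stop date | Pairs | Prior | Concomitant |
|---|---|---|---|
| e < F | 6 + 5 + 4 + 3 + 2 + 1 = 21 | yes | no |
| e = F | 6 | no | no |
| e > F | 6 × 11 = 66 | no | yes |

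The six pairs with e = F are the only unassigned ones among earlier starts. No pair meets both definitions. A medication with s = e = F is concomitant through branch 1, so the gap affects earlier starts only. Pairs with s ≥ L are also unassigned; that may be intended for starts at or after the end of dosing, and it is not part of this point.

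**Do the other rules close the gap?**

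- The rule for completely missing dates does not reach a known stop on Day 1.
- Partial dates are imputed and then returned to the same definitions.
- The Table 1 exceptions for a partial start date run "the stop date is later than Day 1; Otherwise If the stop date is prior to Day 1", which again skips equality. With a full stop date of Day 1 and a start in the same month with the day missing, the default is the first of the month. That is before F unless Day 1 is itself the first, so the record falls into the gap.

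**Which medicines can stop on Day 1 in an eligible subject?** Protocol 3.2 sets restriction intervals, and exclusion criterion 3 bars subjects without the proper washout. The dosing strata place the first dose between 08:00 and 13:00. I assume that intervals are counted back from the first dose; counting from screening, which comes earlier, would only narrow the range.

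- 24 hours or longer (nasal sprays, long-acting oral decongestants, antihistamines, herbal cold products): last use falls before Day 1.
- 12 hours (antitussives, expectorants, immediate-release NSAIDs, short-acting oral decongestants): 08:00 − 12 h = 20:00 the evening before, and 13:00 − 12 h = 01:00 on Day 1. Use on Day 1 is possible only in the first hour after midnight, and only if the first dose is at noon or later.
- 6 hours (lozenges, menthol products, honey): 08:00 − 6 h = 02:00 and 13:00 − 6 h = 07:00, so early-morning use on Day 1 is possible.
- Acetaminophen/paracetamol: occasional use is allowed and no interval is stated.

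**Which analyses use the label?** The primary analysis (SAP 8.1.1, 8.1.2) uses recorded scores whatever other cold medication was taken. The sensitivity analysis (SAP 8.1.3, Appendix D part A) depends on whether a score falls within 4 hours after use. The cough/cold medication summary in SAP 8.1.2 is separate and does not refer to the 7.1 categories. The per-protocol exclusion in SAP 4.4.4 item f refers to the prohibited list. Only the prior and concomitant tables depend on the label.

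**After the change.** Replace branch 2 by s < F and e ≥ F. The six pairs become concomitant. No earlier start is then unassigned, and still no pair is in both categories.

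**The case against.** The case against accepts the literal gap and disputes its weight. Most of that stands.

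- A reader might infer that Day 1 is the most likely stop date for cold medicines in use at entry, because subjects are told at that visit to avoid them. The documents do not support this. Most such medicines must have been stopped earlier for the subject to qualify, and SAP Appendix C classes a breach of exclusion criterion 3 as a significant deviation.
- A reader might also infer that the omitted records weaken the judgement of whether other treatment explains the efficacy result. That goes too far. The plan has separate tools for that question, none of which uses the prior/concomitant label. Use before randomization should balance between arms in expectation, and the ANCOVA adjusts for Baseline NSS taken on Day 1 before the first dose.
- Nothing disappears from the report, because every medication is listed.

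What the objection does not remove is the wrong rule. No text in either document assigns these records, and two planned tables will be incomplete if the rule is followed as written.

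**Conclusion.** The concern holds as a boundary error in a stated definition, and it is minor. All records with an earlier start and a stop on the first dosing date are left out of both class tables; no other earlier-start record is. How many subjects have such a record cannot be derived, since the documents give no medication data. For eligible subjects it should be mainly acetaminophen/paracetamol and early-morning use of products with a 6-hour restriction.

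This rests on two assumptions: that classification is by calendar date, as SAP 7.1 words it, and that a course of use is one record running from an earlier start to a Day 1 stop. If each intake were its own record, a Day 1 intake would already be concomitant through the first branch. The point supports no claim of bias in the treatment effect, its p-value or any analysis population.

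**What to change.** In SAP 7.1, keep the prior definition and the first branch of the concomitant definition unchanged. In the second branch, change the stop-date condition from *after* to *on or after* the first dosing date. The first branch must stay: a rewrite that defines concomitant only through earlier starts would lose medications begun during treatment.

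The cost is a few words in the SAP and one comparison operator in the program, best made before unblinding. The downside is that a medicine last taken on Day 1 shortly before the first dose is counted as concomitant. The first branch already does this for medicines both started and stopped on Day 1, so the change makes the two branches consistent.

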4.5. Withdrawal/ Stopping Criteria

A subject may withdraw from the study at any time at his/her own request, or may be withdrawn at any time at the discretion of the Investigator for ethical, safety, behavioral or administrative reasons. If a subject withdraws or is withdrawn from the study, all human biological samples collected before they left will be analyzed and reported unless the subject requests otherwise. A subject may request for their human biological samples to be destroyed. In these cases, the Investigator must document this in the site study records and the samples should not be used for any further research.

The following circumstances require discontinuation of study treatment and/or premature subject withdrawal:

- Subject did not meet study criteria
- Protocol violation that may impact the outcome of the study and/or subject's safety
- Withdrawal of informed consent
- Unblinding of the subject
- Subject lost to follow-up
- Pregnancy
- Death
- Use of disallowed concomitant medications (see Section 3.2.)

If the reason for removal of a subject from the study is an AE or an abnormal laboratory test result, the principal specific event or test will be recorded on the

Document Name	CCI	Protocol B_Final_Amendment 4_Clean_QA Review		
Type	Version	Document Identifier	Effective Date	
elido_clinical_doc	1.0; CURRENT; Most-Recent; Effective	090032d580d43d4b	19-May-2017 09:57:58	
Reason For Issue	Auto Issue			

electronic case report form (CRF). If a subject is withdrawn from the study because of a product limiting AE, thorough efforts should be clearly made to document the outcome. Any AEs ongoing at the final visit will be followed up until resolved, the condition stabilizes, is otherwise explained, or the subject is lost to follow-up.

The following actions must be taken in relation to a subject who fails to attend the clinic for a required study visit:

- The site must attempt to contact the subject and re-schedule the missed visit as soon as possible.
- The site must counsel the subject on the importance of maintaining the assigned visit schedule and ascertain whether or not the subject wishes to and/or should continue in the study.
- In cases where the subject is deemed 'lost to follow up', the Investigator or designee must make every effort to regain contact with the subject (where possible, at least 2 telephone calls). The contact attempt should be documented in the subject's record.

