- Should the subject continue to be unreachable, only then will he/she be considered to have withdrawn from the study with a primary reason of "Lost to Follow-up".
- All subjects will not be permitted any use of disallowed concomitant medications. The subject will be discontinued from study treatment if the subject takes more than one dose of disallowed concomitant medications. All medications, procedures and significant non-drug therapies (including physical therapy and blood transfusions) administered after the subject starts study treatment must be listed in the CRF.

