6.4. Visit 2 – End of Study /Early Termination (Day 8)

6.4.1. Self-Assessment of Common Cold Symptoms

Upon awakening on Day 8, subjects will perform a self-assessment of common cold symptoms and record it in the e-diary. See Section 6.1.7. for details on Common Cold Symptoms and the severity grading.

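### SAP 7.1 ends the concomitant-medication window at the last study dose, so a medication started after that dose is neither prior nor concomitant and is missing from the by-arm ATC table (minor).

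*SAP*

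**What the plan says.** SAP 7.1 (Prior and Concomitant Medications) defines two classes.

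- Prior: "prior medications are defined as any medication with a stop date that is prior to the initial study drug dosing date".
- Concomitant, first limb: "any medications with a start date on or after the initial study drug dosing date, but prior to the last study drug dosing".
- Concomitant, second limb: "any medications with a start date prior to the initial study drug dosing date and a stop date after the initial study dosing date".

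The one default into the concomitant class is for records with no date at all: "Medications with completely missing dates will be included in the concomitant medication summary". The classes feed a table by arm on the Safety set: "The number and percentage of subjects receiving prior and concomitant medications will be displayed by medication classes" at ATC levels 1 and 2. A listing of every medication is also planned.

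The protocol sets no limit at the last dose. Section 4.5 says that medicines and other therapies "administered after the subject starts study treatment must be listed in the CRF". Section 6.4.7 still records changes in concomitant medication at Visit 2 on Day 8. Section 9.3.5.2 plans the by-arm ATC summary without any cutoff at the last dose. Symptom recording also runs past the last dose: "Upon awakening on Day 8, subjects will perform a self-assessment of common cold symptoms" (Protocol 6.4.1).

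**The concern.** The two classes do not cover all on-study use. A medication first taken after the last dose did not stop before the first dose, did not start before the last dose and did not start before the first dose. It meets none of the three conditions, so it drops out of the table although it was collected.

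The treatment of dates is also uneven. A record with no dates is counted, and a start with only the day missing can be imputed to Day 1 under Table 1 and so be counted. A late start with a complete date is dropped.

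At stake is the completeness of the by-arm description of other medication. A subject who stops the spray and then turns to another remedy can be absent from that table.

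**Working it through.** The plan gives no figure to reproduce. The check applies the SAP 7.1 rules literally to test cases.

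**Inputs.**
- F = first dosing date, Day 1.
- L = last study drug dosing. For a completer this is on Day 7, with final assessments on Day 8 (Protocol 4.7).
- Nominal final dose on Day 7: first dose at 07:00, then three more at 4-hour intervals (Protocol 5.2.2), so 07:00 + 3 × 4 h = 19:00. The other clock times below are illustrative.

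**Rules.**
- Prior: stop date < F.
- Concomitant (a): F ≤ start < L.
- Concomitant (b): start date < F < stop date.

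The upper bound in (a) can be read in two ways. The rule compares a start date, and Table 1 imputes dates only, which points to a date comparison. The SAP attaches the word date to the initial dosing but not to the last dosing, so a date-plus-time comparison is also possible.

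| Case | Date reading | Date-plus-time reading |
|---|---|---|
| Completer, start Day 6 | concomitant | concomitant |
| Completer, start Day 7 10:00, before the last dose | neither | concomitant |
| Completer, start Day 7 21:00 | neither | neither |
| Completer, start Day 8 07:00 | neither | neither |
| Last dose Day 3 15:00, start Day 2 | concomitant | concomitant |
| Last dose Day 3 15:00, start Day 3 10:00 | neither | concomitant |
| Last dose Day 3 15:00, start Day 3 18:00 | neither | neither |
| Last dose Day 3 15:00, start Day 4 | neither | neither |
| Single dose Day 1 09:00, start Day 1 14:00 | neither | neither |

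**Result.** On the date reading, a subject whose last dosing day is Day d has starts counted on Days 1 to d − 1 only. A completer (d = 7) has Days 1 to 6 counted and Days 7 and 8 not. A subject dosed on Day 1 only has no day counted. On the date-plus-time reading, only starts after the last dose are lost. That loss occurs on both readings.

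**What else uses the classes.**
- Primary mITT analysis (SAP 8.1.2): recorded scores are used whatever cough/cold medication was taken.
- Cough/cold medication summary by arm (SAP 8.1.2): not tied to the SAP 7.1 classes. Its own window is not stated.
- 4-hour sensitivity analysis (SAP 8.1.3, Appendix D): defined by the use of a medication, not its class.
- PP exclusion (SAP 4.4.4, item f): prohibited medication on Days 1 to 4.
- Listing: all medications.

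None of these refers to the prior/concomitant definition.

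**Bearing on the endpoints.** Scores are recorded immediately before each dose (Schedule of Events, note f), so a start after the last dose comes after the last pre-dose score. For a completer only the Day 8 awakening score follows, and no primary or secondary endpoint uses Day 8. For an early stopper, data missing after dropout are not imputed in the primary analysis. The remaining exceptions are narrow: a diary entry made without a dose, or an assessment at early termination.

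**The case against.** The strongest defence is that limiting *concomitant* to medication begun while study drug is being taken is a coherent on-treatment definition. On that view the fault is a missing label for post-treatment use in a descriptive table, and the use that matters for the symptom scores is reported in the separate cough/cold summary. Most of this stands, and it is why the point is minor. It does not remove the point: no post-treatment class is defined, the protocol treats medication changes at Visit 2 as concomitant, and the cough/cold summary would not show other kinds of medication.

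A reader might infer more than the documents support:

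- *That interpretation of ANSS and ATSS depends on this table.* Starts after the last dose almost never precede a score that enters those endpoints, and the analyses that deal with other medication do not use the classes.
- *That a medication which ended treatment is always lost.* It is lost only if it started after the last dose, or on the last dosing day under the date reading. Protocol 4.5 stops treatment after more than one dose of a disallowed medication; if study dosing continued after the first use, that start may precede the last dose and be counted. Protocol 3.2 and the list in 4.5 state no such threshold, but the gap does not depend on which wording applies.
- *That two of the eight diary days are always lost for a completer.* This holds only on the date reading.
- *That the undercount differs between arms.* It could, but neither document gives a figure on this.

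**Conclusion.** The gap is real on either reading, and neither document closes it. Starts between the last dose and the end-of-study or early-termination visit are unclassified and leave the ATC table. Under a date comparison, starts earlier on the last dosing day go too. The SAP is thereby narrower than the protocol's recording and planned summary of concomitant medication.

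Severity is minor. The consequence is an undercount in one descriptive Safety-set table, with no effect on the primary result. The number of records affected cannot be estimated, because the documents give no rate of late-starting medication. The conclusion assumes that SAP 7.1 is programmed as written and that no unstated convention sweeps late starts into the concomitant class.

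**What to change.** In SAP 7.1, define concomitant medication as any medication with a start date from the first dosing date through the end-of-study or early-termination visit, or one started before the first dose and continuing after it. If the on-treatment distinction is wanted, flag starts after the last dose separately within the same table.

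With this change every start on Days 1 to 8 up to the visit is classified. Moving the bound only to the last dosing date, inclusive, would recover that day but still omit later starts.

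The cost is one sentence and one changed date comparison, with no new data. The downside is that the table will include a few medications begun after the last dose, which the flag would make visible.
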